Primary hypothesis: Women that undergo cesarean delivery at KK Women's and Children's Hospital, Singapore, who has higher pain score upon local anesthetic injection, will have higher risk of getting postcesarean pain.

Primary aim: To determine whether there is a positive correlation between pain on local anesthetic injection and post-Cesarean pain scores in women that undergo cesarean delivery at KK Women's and Children's Hospital, Singapore.

Secondary hypothesis (1): Women that undergo cesarean delivery at KK Women's and Children's Hospital, Singapore, who has mechanical temporal summation (MTS>0), will have higher risk of getting post-cesarean pain.

Secondary aim (1): To determine whether there is a positive correlation between mechanical temporal summation and post-Cesarean pain scores in women that undergo cesarean delivery at KK Women's and Children's Hospital, Singapore.

Secondary hypothesis (2): Women that undergo cesarean delivery at KK Women's and Children's Hospital, Singapore, who has higher anxiety score, anticipated pain score and/or anticipated medication need, will have higher risk of getting post-cesarean pain.

Secondary aim (2): To determine whether there is a positive correlation between higher anxiety score, anticipated pain score and/or anticipated medication need and post-Cesarean pain scores in women that undergo cesarean delivery at KK Women's and Children's Hospital, Singapore.

Exploratory Aim: To examine the correlation between medical history (presence of hyperemesis gravidarum, motion sickness, PONV etc.), demographical data and the incidence of post-operative emesis.

F3. Please briefly describe the background to the current study proposal. Critically evaluate the existing knowledge and specifically identify the gap that the proposed study is intended to fill.

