clinically feasible, while local anesthetic injection is already part of the standard protocol for initiating spinal or epidural anesthesia. And although all of the questionnaires appear to have some potential for clinical use, the three simple questions appears to be the most useful due to its brevity while maintaining acceptable sensitivity and specificity for identifying patients who will fall in the upper 20th percentile of pain needs [18]. Local anesthetic injection and the “three simple questions” are both promising techniques that could lead to greater post-Cesarean pain management, but neither has yet to be validated outside of their respective institution of origin. Therefore, the purpose of this study is to evaluate the effectiveness of these two measures for the prediction of postoperative pain in women undergoing Cesarean delivery at KKH.

While numerous studies have investigated risk factors for postoperative nausea and vomiting in the general surgical population, there are relatively little data in the obstetric patient population. We will collect information about potential risk factors for post-operative nausea and vomiting (PONV), and assess for association with the occurrence of PONV. We will collect information about the following factors: history of PONV after CD, history of PONV after non obstetric surgery, history of morning sickness, history of hyperemesis gravidarum, history of motion sickness, smoking history, occurrence of intraoperative nausea and vomiting, and exteriorization of the uterus.

F4. Please provide a list of relevant references.

1. Hamilton, B.E., et al., Births: Final Data for 2014. *Natl Vital Stat Rep*, 2015. **64**(12): p. 1-64.
2. Eisenach, J.C., et al., Severity of acute pain after childbirth, but not type of delivery, predicts persistent pain and postpartum depression. *Pain*, 2008. **140**(1): p. 87-94.
3. Niklasson, B., et al., Risk factors for persistent pain and its influence on maternal wellbeing after cesarean section. *Acta Obstet Gynecol Scand*, 2015. **94**(6): p. 622-8.
4. Ip, H.Y., et al., Predictors of postoperative pain and analgesic consumption: a qualitative systematic review. *Anesthesiology*, 2009. **111**(3): p. 657-77.
5. James, A.H., et al., Venous thromboembolism during pregnancy and the postpartum period: incidence, risk factors, and mortality. *Am J Obstet Gynecol*, 2006. **194**(5): p. 1311-5.

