Our prospective group study will investigate the role of modifiable risk factors and develop a model that would take into account biological and psychological mechanisms to better understand PONV and pain after cesarean surgery. We will identify modifiable risk factors and explore the interplay of psychological and pain pathways will be investigated through targeted selected serotonin, monoamine and oxytocin candidate gene polymorphism with post-operative pain, PONV and postnatal depression. Our study will broaden the current understanding and basic neurobiological mechanisms especially in central sensitisation and central nervous system dysregulation in PONV and post-operative pain. We will validate the role of analgesic interventions and needs in reducing the risk of PONV and post-cesarean pain and change the current clinical practice in the care during cesarean delivery management. The proposed study will guide us in future studies on potential novel risk stratification and identify modifiable risk factors as therapeutic targets.

F7. Long Term Implications of Research

The long term goal of our project is to establish a collaborative care model according to each individual's risk factors and eventually to target specified interventions to minimize the risk of PONV and improve the pain experience after childbirth. The psychobiological model derived from this trial could be the basis of subsequent hypothesis testing in research into modifiable risk factors, as well as, validation of the model in a new population group such as other pain syndromes. This trial would aim to develop prediction and model validation in the long term. We plan to incorporate a longer term follow-up study (2 to 3 years) following this proposal to examine the sustained effect of these risk factors on post-operative pain and depression after childbirth including health sciences outcomes like cost-effectiveness analysis and longer term functional outcomes.

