During cesarean delivery: Surgery, intraoperative and postoperative management will be performed according to standard practice. Data will be collected on heart rate, blood pressure, oxygen saturation, presence of nausea and vomiting and use of wound infiltration. Acute pain in the postoperative care unit (PACU) will be treated at clinician's discretion.

After delivery and before discharge from the hospital: The woman is interviewed at 0 to 48 hours on the pain scores at rest and with movement (sitting up in bed from a supine position) and will be recorded in the nursing electronic records. Other data such as nausea scores, and occurrence of vomiting are also noted. Standard routine monitoring of haemodynamics parameters and pain relief will be done in the ward. Study surveys are continued while patient is comfortable before discharge or till 5-14 days after discharge. The survey for post-delivery health status (HADS, EQ-5D-3L) will take about 10 minutes to complete.

Six - Ten weeks after delivery: The patient will have a phone survey/ online survey at 6 -10 weeks post-delivery with: (1) EPDS (2) Pain Survey (3) Pain Vulnerability (PCS, CSI) (4) Breastfeeding Questionnaire (5) EQ-5D-3L and (6) HADS. Patients with scores on the depression scale consistent with postpartum depression will be referred to their obstetrician or primary care physician for further assessment and management.

F9. Please provide details on sample size and power calculation and the means by which data will be analyzed and interpreted (if applicable).

As an observational study, we will target to enrol for up to 200 consented subjects. The primary hypothesis will be assessed with a Pearson correlation test at $\alpha=0.05$ cutoff for statistical significance. The secondary numeric measures of pain, nausea, and satisfaction will be assessed for correlation with the preoperative measures using a Pearson correlation test. Anticipating that some patients will not require rescue oxycodone, we plan to analyze the time to rescue oxycodone via Kaplan-Meier mean time to event analysis. Dichotomous variables will be assessed via chi-square tests or fisher exact tests.

F10. List all activities that are carried out as part of research in this study. Please state/list all procedures involved in this research study and attach the data collection form (if any) which will be used for CIRB review.

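### F9 tests post-operative emesis against one categorical factor at a time, which does not support the risk-factor and model claims in F1 and F6

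*Protocol*

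**What the plan says.** The protocol describes the emesis question in four places and its analysis in one.

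- **F1 (abstract)** gives finding the risk factors for emesis after cesarean delivery as an aim.
- **F2 (exploratory aim)** relates medical history and "demographical data and the incidence of post-operative emesis".
- **F3** lists eight candidate factors: two histories of PONV (after cesarean delivery and after other surgery), then "history of morning sickness, history of hyperemesis gravidarum, history of motion sickness, smoking history, occurrence of intraoperative nausea and vomiting, and exteriorization of the uterus". It asks for association with PONV.
- **F6** says the study will "develop a model that would take into account biological and psychological mechanisms to better understand PONV and pain after cesarean surgery", and adds: "We will identify modifiable risk factors". F7 goes on to speak of a psychobiological model derived from this trial.
- **F9** names the methods: Pearson correlation for the primary hypothesis, Pearson for numeric secondary measures including nausea, Kaplan-Meier for time to rescue oxycodone, and for the rest "Dichotomous variables will be assessed via chi-square tests or fisher exact tests".

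Emesis incidence is dichotomous, so the last method is the one that applies to it. No regression or other multivariable method is planned anywhere in the protocol.

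**The concern.** A contingency-table test answers whether emesis is more frequent in women with a given factor. It does not answer whether the factor matters once its neighbours are known. Several F3 factors plausibly travel together: hyperemesis is the severe end of morning sickness, and motion sickness and prior PONV may reflect one susceptibility. Tested singly, a history that only marks another one will show an association and may be reported as a risk factor, which is how F1 and F6 intend the results to be read.

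Age, with an eligible range of 21-50 years in I1, enters such a test only if it is grouped, and grouping loses information. The team's own pilot in F5 did otherwise: it reported independent risk factors, with age as an odds ratio per 5 years. At stake is a list of emesis risk factors that later risk stratification (F6, F7) would build on.

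**Working it through.** **The plan's own figures.** F9 says "we will target to enrol for up to 200 consented subjects" and sets alpha at 0.05 for the primary test. It gives no power, effect size or emesis rate, so there is no emesis figure to reproduce.

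**Inputs.** From the protocol: n = 200. Assumed: alpha 0.05 two-sided for these tests too; two histories, A and B, each in 30% of women; emesis in 20% of women without A; only A acts, with odds ratio (OR) 2, 3 or 4; latent correlation of A and B of 0.3, 0.5 or 0.7.

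**1. One case by hand (correlation 0.5, OR 3).**
- Thresholding two normals with correlation 0.5 at 30% prevalence gives P(A|B) = 0.523 and P(A|no B) = 0.205.
- Emesis with A: odds 0.25 × 3 = 0.75, so the risk is 0.75/1.75 = 0.4286.
- Emesis with B: 0.20 + 0.523 × 0.2286 = 0.319. Without B: 0.20 + 0.205 × 0.2286 = 0.247.
- Marginal OR of B: (0.319/0.681)/(0.247/0.753) = 1.43, although B has no effect of its own.
- Overall risk: 0.7 × 0.20 + 0.3 × 0.4286 = 0.2686. SE of the difference with 60 v 140 women: √[0.2686 × 0.7314 × (1/60 + 1/140)] = 0.0684.
- z = 0.0726/0.0684 = 1.06. The test rejects with probability about 19%.

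**2. Simulation (3,000 studies per setting).** Uncorrected chi-square for B alone, against B in a two-predictor logistic regression with A (Wald test):

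| Latent correlation | OR of A | Chi-square flags B | Adjusted analysis flags B |
|---|---|---|---|
| 0.3 | 2 / 3 / 4 | 6% / 10% / 13% | 4% / 5% / 5% |
| 0.5 | 2 / 3 / 4 | 9% / 20% / 26% | 5% / 4% / 5% |
| 0.7 | 2 / 3 / 4 | 17% / 35% / 54% | 5% / 4% / 5% |

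The hand result (19%) agrees with the simulated 20%. With no overlap both methods stay near 5%. The size depends on the emesis rate and the version of the test: with OR 2.5, correlation 0.5-0.7 and an overall emesis rate of 10%, the chi-square figure is 11-17%, or 7-12% with continuity correction.

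**3. A numeric predictor.** If one were split at its median, with OR 1.5 per SD, power at n = 200 would be 44% against 62% when kept continuous (20% emesis at the mean), and 55% against 72% (30%). Over OR 1.4-1.6 the loss is about 14-20 percentage points.

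**4. What 200 women can carry.** Terms: age 1; none/morning sickness/hyperemesis 2; PONV after cesarean delivery (yes/no/no such surgery) 2; PONV after other surgery, coded likewise, 2; motion sickness 1; smoking as yes/no 1. Total 9. Events per term = 200 × rate / 9:

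| Assumed emesis rate | Events | Events per term |
|---|---|---|
| 10% | 20 | 2.2 |
| 20% | 40 | 4.4 |
| 30% | 60 | 6.7 |
| 40% | 80 | 8.9 |

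**The case against.** The strongest reply is that the tests suit the aim as F2 and F3 word it. The aim is exploratory and asks for correlation or association, and a marginal OR of 1.43 is a real marginal association. A reader might infer that the chi-square results would be false positives. The documents do not support that: the error arises only when the results are read as separate risk factors or as a model. This reply stands for F2 and F3 but does not cover F1 and F6.

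Other stronger readings also fail:

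- **That F9 cuts age.** It does not say so. It leaves open how a numeric predictor is set against a yes/no outcome, so the median-split figures show what grouping would cost and do not describe a stated plan.
- **That all of PONV gets contingency tables.** F9 also says: "The secondary numeric measures of pain, nausea, and satisfaction will be assessed for correlation with the preoperative measures using a Pearson correlation test". Nausea scores can therefore meet numeric predictors uncut, though still one at a time.
- **That a regression on age and histories would be the F6 model.** F6 speaks of biological and psychological mechanisms and of candidate genes, while F8, F10 and F11 list no genetic sampling. Hence the F6 wording needs attention as well.

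F6 answers a form question on implications, so it is a weaker commitment than an aim, and a separate SAP may add a model. But F9 is where the form asks how data will be analysed, and it names a method. A SAP that follows F9 cannot produce the model, and one that produces it departs from F9.

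**Conclusion.** The point holds as a mismatch between a stated method and a stated purpose. F9 gives unadjusted, one-factor tests for emesis, while F1 and F6 promise risk factors and a model. The 6-54% range against about 5% shows how large the effect can be; it is not a forecast. Overlap, prevalence, effect sizes and emesis rate are all assumed, and at low overlap or a low emesis rate the excess is small. The figure of about 5% comes from a two-predictor model and does not show how a nine-term model would perform. The matter concerns an exploratory aim, is cheap to improve, and leaves the primary Pearson analysis untouched.

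**What to change.** In F9, add one prespecified exploratory multivariable logistic regression for post-operative emesis:

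- age as a continuous term;
- morning sickness and hyperemesis as one three-level variable;
- each prior-PONV history with a level for no such prior surgery, so that no women are dropped (I1 admits nulliparous women, for whom PONV after cesarean delivery is undefined);
- motion sickness and smoking included;
- intraoperative nausea and vomiting left out of the main model, because it follows the histories and may lie on their path to the outcome;
- a penalised (Firth) fit, with the number of terms limited by the observed number of events under a rule fixed before associations are seen.

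F3 also lists exteriorization of the uterus. State whether it enters; it would be a tenth term.

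Keep chi-square/Fisher as unadjusted description. Reword F6 and F7 so that the model claimed goes no further than this analysis.

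The cost is wording only: no new data, visits or participants. The price is wider intervals than the one-factor tests give and few events per term, so the results must be labelled exploratory.

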E4. Who will be responsible for research-related costs? For sponsored studies, please list the costs that will be borne by the sponsor.

Anaesthesiology ACP Pilot Research Grant

Section F: Research Methodology

F1. Please provide an abstract of your proposed research (Up to 300 words).

Approximately 1 in 5 women who undergo cesarean delivery would suffer from severe post-operative pain, which may further increase their risks from developing postpartum depression. Predictive factors such as pre-operative pain, age and anxiety could significantly contribute to post-operative nausea and vomiting (PONV) and pain in general surgery, however little information is available with regards to cesarean delivery. Previous studies demonstrated that pain scores upon local anesthetic injection is positively correlated to post-cesarean pain scores. Additionally, anxiety, anticipated post-operative pain score and anticipated medication need are also found to be promising risk factors to postcesarean pain management.

We aim to investigate the risk factors of causing post-operative emesis after cesarean delivery, and to reaffirm that there is a positive correlation between pain on local anesthetic injection, presence of mechanical temporal summation (MTS) and post-Cesarean pain scores. We will recruit 200 parturients undergoing cesarean delivery at KK Women's and Children's Hospital and requiring regional anesthesia. Pain and anxiety assessment will be conducted via visual analogue scoring (VAS), MTS assessment and a series of questionnaires. After the delivery, all patients will be given appropriate analgesia, and the pain score at movement will be recorded. Secondary outcomes include pain scores at rest, analgesia consumption, time-to-first-rescue analgesia, opioid-related side effects, patient satisfaction and postpartum depression.

This proposal will determine the clinical relevance of pre-operative determinants for post-cesarean pain management in local context. This would help us discover new risk management strategies and identify modifiable treatment. We hope that this will serve as a guideline for consistent and reliable delivery of care while enhancing the effectiveness and patient satisfaction in obstetrics pain management.

F2. What are the specific aims and hypothesis of this study?

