We conducted a pilot cohort study involving 479 women who delivered at KK Hospital from November 2010 to October 2013 who had psychological assessment. The analgesic outcomes were analysed retrospectively. PND diagnosis was made using psychiatrist diagnosis. PND was present in 12.9% (62/479). The incidence of PND was 10.0% (33/329) of women who received epidural analgesia and 19.3% (29/150) of those who choose non-epidural analgesia (p=0.0149). The independent risk factors included the absence of epidural analgesia being associated with increased risk of PND (OR 1.95, 95%CI 1.04-3.66, p=0.0367). Increasing age was associated higher risk of PND (OR 1.56, 95%CI 1.15-2.14, p=0.005, every 5 years increase). Psychological factors associated with PND were family history of depression (OR 11.1, 95%CI 4.23-29.75, p<0.0001), history of depression (OR 10.61, 95%CI 2.34-58.15, p=0.003) and previous history of PND (OR 9.42, 95%CI 3.7-24.54, p<0.0001). Though the findings of this observational study is intriguing, a more definitive trial is required to provide strong evidence for this observation. Furthermore, the outcomes for PP after childbirth were not available.

Submission Date: 31-May-2018

The principal investigator has recently published an invited review article as the senior author in a peer reviewed journal: Trends in Anaesthesia and Critical Care on 'Childbirth pain and Postpartum Depression'. The article illustrates the expanded role of the anaesthetists beyond pain relief and provides an argument for the discipline to take a greater role in patient care during childbirth. The accompanying commentary by Vuilleumier et al titled 'Is Birthing pain the trigger of postpartum depression? A commentary on Childbirth pain and Postpartum Depression' is evidence of the overwhelming interest in this topic. The authors suggested that further work is needed in order to understand how pain and depression relate to each other and that improved attention to helping women achieve desired pain control during and after childbirth may have far reaching benefits.

Studies Related to Persistent Pain and Childbirth Pain

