Patients will be asked to rate, using a 0-10mm visual analog scale (VAS), their surgical anxiety level ("On a scale of 0-100, with 0 being not anxious at all to 100 being extremely anxious, how anxious are you about your upcoming surgery?"), their anticipated pain (On a scale of 0-100, with 0 being no pain at all and 100 being pain as bad as you can imagine, how much pain do you anticipate experiencing after your upcoming surgery?"), and using a categorical scale, their anticipated pain medication need ("On a scale of 0 to 5, with 0 being none at all, 1 being much less than average, 2 being less than average, 3 being average, 4 being more than average, and 5 being much more than average, how much pain medication do you anticipate needing after your upcoming surgery?").

Study survey will be administered upon recruitment in antenatal clinic or delivery suite or till 5-14 days after discharge whenever patient is comfortable. It includes Edinburgh Postnatal Depression Scale (EPDS), Pain Catastrophizing Scale (PCS), Central Sensitisation Inventory (CSI), EQ-5D-3L and HADS. The estimated duration of the surveys is about 30 minutes.

Mechanical temporal summation (MTS) assessment using a 180 gram von Frey filament applied to the patient's arm, as demonstrated by Weissman-Fogel, et al.[20], will be done prior to surgery and results recorded. The anesthetic technique will be standardized using the current standards of care. All women will receive antacid prophylaxis with 30 ml sodium citrate. The spinal anesthesia administered will be standardized doses of intrathecal hyperbaric bupivacaine (10.5-12 mg), fentanyl (15 mcg), and preservative-free morphine (100 mcg). Before placing the spinal anesthetic, the skin at the site will be infiltrated with 2-5 ml 1.0% lidocaine as per standard practice. It has been shown that the words used during local anesthetic injection can influence patient's subjective experience of pain, so prior to local anesthetic injection we will use a standardized script to inform patients that local anesthetic is about to be given: "I am now giving you the numbing dose." After the injection is completed and the needle is removed, the anesthesiologist will use a standardized script, "From 0 to 10, where 0 is no pain and 10 is the worst pain imaginable, how much did this procedure hurt?" Patient's responses will be recorded.

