The duration of study period for each participant can last about 17 weeks. Below are the main time points for the study activities:

Before surgery (duration: 4 weeks):

- Patient screening and recruitment before the surgery: gestational age week 36 and above
- Baseline Demographic data collection
- Survey and data collection (EPDS, pain score, vital signs, HADS score, EQ-5D-3L, MTS, "three questions", pain vulnerability (PCS, CSI))

After surgery (duration of labour till 5-14 days after discharge: ~19 days):

- Pain assessment, survey and data collection (pain score, vital signs, HADS score, EQ-5D-3L, analgesia usage, occurrence of vomiting, and nausea scores)

Follow up phone call survey at 6 - 10 weeks after delivery (duration: 10 weeks):

- Phone survey/ Online survey and data collection (EPDS, breastfeeding, HADS score, EQ-5D-3L, pain score, and pain vulnerability (PCS, CSI))

F11. Please describe the participant's visits (frequency and procedures involved). For studies with multiple visits, please attach study schedule.

There will be 3 visits in total. The duration of study period for each participant can last about 17 weeks. Below are the main time points for the study activities:

Visit 1-Before surgery (duration: 4 weeks):

- Patient screening and recruitment before the surgery: gestational age week 36 and above
- Baseline Demographic data collection
- Survey and data collection (EPDS, pain score, vital signs, HADS score, EQ-5D-3L, MTS, "three questions", pain vulnerability (PCS, CSI))

Visit 2-After surgery (duration of labour till 5-14 days after discharge: ~19 days):

- Pain assessment, survey and data collection (pain score, vital signs, HADS score, EQ-5D-3L, analgesia usage, occurrence of vomiting, and nausea scores)

Visit 3-Follow up phone call survey at 6 - 10 weeks after delivery (duration: 10 weeks):

- Phone survey/ Online survey and data collection (EPDS, breastfeeding, HADS score, EQ-5D-3L, pain score, and pain vulnerability (PCS, CSI))

F12. Discuss the potential difficulties and limitations of the proposed procedures and alternative approaches to achieve the aims.

There will be drop out in the follow up phone survey. However, the withdrawal rate has been accounted for.

F13. What are the potential risks to participants?

During the MTS pain assessment, a test would involve the repeated sensation of pinprick testing for increased sensitivity of pain to pinprick in some individuals.

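### Postpartum depression is a secondary outcome, but F9 names only unadjusted tests, so a crude link with pain or anxiety may reflect depression already present before delivery

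*Protocol*

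**What the plan says.** Section F1 of the protocol ends its list of secondary outcomes with "opioid-related side effects, patient satisfaction and postpartum depression". No aim or hypothesis in F2 concerns depression.

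F9 sets out the analysis. The primary hypothesis gets a Pearson correlation. For the rest, "The secondary numeric measures of pain, nausea, and satisfaction will be assessed for correlation with the preoperative measures using a Pearson correlation test". Depression and EPDS are not in that list. Time to rescue oxycodone gets a Kaplan-Meier analysis. The remaining rule is "Dichotomous variables will be assessed via chi-square tests or fisher exact tests". F9 names no covariate and no multivariable model for any outcome.

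EPDS is measured twice. F10 and F11 place the first measurement before surgery: "Survey and data collection (EPDS, pain score, vital signs, HADS score, EQ-5D-3L, MTS". F8 places the second later: "The patient will have a phone survey/ online survey at 6 -10 weeks post-delivery with: (1) EPDS". For the survey that contains the first EPDS, however, F8 gives a wider window: "Study survey will be administered upon recruitment in antenatal clinic or delivery suite or till 5-14 days after discharge whenever patient is comfortable". An EPDS of 13 or more appears in F13 as a trigger for advising assessment, not as an analysis definition.

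The pilot cohort in F5 reports, among the psychological factors associated with postnatal depression, "history of depression (OR 10.61, 95%CI 2.34-58.15, p=0.003". The exclusion criteria in I2 do not mention depression.

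**The concern.** Nothing in an observational study balances antenatal mood across levels of pain or anxiety. A woman who is already depressed before surgery may report more anxiety and more pain, and may score high on EPDS again at 6-10 weeks. A test that ignores her starting point attributes that persistence to the pain or the anxiety.

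This matters for what the study wants to say. F6 promises to identify modifiable risk factors as therapeutic targets and to model psychological mechanisms. An association that could be pre-existing depression seen twice would not support that. The instrument needed to separate the two is already on the schedule, and the pilot in F5 reported independent risk factors, so F9 is less demanding than the team's own earlier work.

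**Working it through.** **There is no figure of the plan's own to reproduce.** F9 gives a target of up to 200 women with no power or effect size for any outcome.

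**Inputs from the protocol**
- Enrolment up to 200 (F9).
- Response to a 6-10 week survey in the site's earlier trial: 134/176 = 76.1% (F5). Expected EPDS returns: 200 × 0.761 = 152.
- Postnatal depression in the pilot: 62/479 = 12.9% (F5). Expected cases: 152 × 0.129 ≈ 20.
- Severe acute pain in about 1 in 5 (F3).
- Odds ratio (OR) of prior depression with postnatal depression: 10.61 (F5). It is a proxy here, because history of depression is not the same as antenatal EPDS.

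**Assumptions not in the protocol**
- Prevalence of antenatal depression C: 10% or 15%.
- OR of C with severe pain: 1, 2 or 3.
- OR of C with postpartum depression: 5 or 10.61.
- Severe pain (yes/no) as the exposure; test two-sided at 0.05.

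**Bias when pain has no true effect.** The crude risk in each pain group is P(dep | C=0) × P(C=0 | group) + P(dep | C=1) × P(C=1 | group), with margins fixed at 20% severe pain and 12.9% depression.

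*Mildest confounded case* (prevalence 10%, ORs 2 and 5). P(C) is 0.158 with severe pain and 0.086 without. P(dep) is 0.364 with C and 0.103 without.
- Severe pain: 0.103 × 0.842 + 0.364 × 0.158 = 0.144
- Otherwise: 0.103 × 0.914 + 0.364 × 0.086 = 0.125
- Crude OR = (0.144/0.856)/(0.125/0.875) = 1.18

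*Strongest case* (prevalence 15%, ORs 3 and 10.61). P(C) is 0.284 and 0.117. P(dep) is 0.452 and 0.072.
- Severe pain: 0.072 × 0.716 + 0.452 × 0.284 = 0.180
- Otherwise: 0.072 × 0.883 + 0.452 × 0.117 = 0.116
- Crude OR = 1.66

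**False-positive rate in the harmful direction.** Group sizes are 30.4 and 121.6. The SE of the risk difference under the null is √[0.129 × 0.871 × (1/30.4 + 1/121.6)] = 0.068. The rate is Φ[(difference − 1.96 × 0.068)/SE under the actual risks].
- Mildest: (0.019 − 0.133)/0.070 = −1.62, giving 5%.
- Strongest: (0.063 − 0.133)/0.075 = −0.93, giving 18%.

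| OR of antenatal depression with severe pain | Crude OR, no true effect | False positives, harmful direction |
|---|---|---|
| 1 | 1.00 | 2.5% |
| 2 | 1.18-1.37 | about 5-10% |
| 3 | 1.31-1.66 | about 8-18% |

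**Precision, yes/no outcome.** Over 24 scenarios (those above, each with a true pain OR of 1 or 3), the SE of the log OR at 152 women is 0.51-0.61 crude and 0.54-0.66 adjusted. The adjusted SE is larger every time, by about 3-14%. With a true OR of 3 and no confounding, power is 44-53% crude and 46-53% adjusted.

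**Precision, numeric EPDS.** Assume the predictor correlates 0.3 with baseline EPDS, baseline EPDS correlates r with follow-up EPDS, and there is no direct effect. The ratio of adjusted to crude SE is √[(1 − r²)/(1 − 0.3²)] / √[1 − (0.3r)²].
- r = 0.4: 0.961/0.993 = 0.97
- r = 0.5: 0.908/0.989 = 0.92
- r = 0.6: 0.839/0.984 = 0.85

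The linear model's SE is thus about 3-15% smaller.

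**The case against.** F9 never names postpartum depression or EPDS, never dichotomises EPDS for analysis, and states no exposure for it. A reader might infer that the protocol has committed to a chi-square test of depression against pain. It has not; that is the most natural reading of F9, not its text. The gap remains on the other reading, because a numeric EPDS has no analysis in F9 at all.

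The F2 aims concern pain and, as exploratory, emesis, and are framed as correlation. Confounding matters less for pure prediction. That stands, and it limits the weight of the point, but F6 goes beyond prediction.

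Covariate adjustment is often left to an analysis plan, and one may exist. This is fair as far as it goes. F9 is not silent, though: it states the tests, and those for dichotomous outcomes are unadjusted.

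Two stronger readings are tempting and fail. The first is that an unadjusted test loses precision. For a yes/no outcome it does not, since the adjusted log OR had the larger SE in all 24 scenarios. The second uses correlations of 0.3 and 0.5 to obtain a spurious r of 0.3 × 0.5 = 0.15, declared significant about 45% of the time at 152 women. The arithmetic is right, but it describes a Pearson test on numeric EPDS, which F9 does not list, under assumed correlations. It does not size the chi-square or Fisher test.

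Finally, a clean baseline is not assured. Under the F8 window the first EPDS may be taken after delivery, when it may lie on the path from pain to depression. That is correct, and the fix has to deal with it.

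**Conclusion.** The point holds as a matter of confounding. For an outcome the protocol lists as secondary, the only method in F9 that could cover it as yes/no is unadjusted, while a strong prior predictor is known from the team's pilot and a baseline measure is scheduled. Under the stated assumptions a null pain effect would appear as an OR of about 1.2-1.7, with harmful-direction false positives at about 5-18% rather than 2.5%. The size depends on a link between antenatal depression and the predictor that the protocol does not quantify; with no link the bias is zero. The documents do not support a claim that precision is lost in general: a modest gain is expected only for a linear model of EPDS. As a secondary outcome outside the F2 aims, this is worth correcting but does not threaten the primary analysis.

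**What to change.** In F9:
- Name the depression outcome and the predictor or predictors it is tested against.
- Analyse EPDS at 6-10 weeks by linear regression on the predictor, with pre-delivery EPDS as covariate.
- As a supportive analysis, model EPDS of 13 or more by logistic regression with the same single covariate. With about 20 expected cases, a longer covariate list is not safe.
- Accept only an EPDS taken before delivery as baseline.
- Give confounding as the reason for adjustment.

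Reconcile F8, which lets the first survey run until after discharge, with F10 and F11, which place it before surgery.

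The change should stop at this outcome. HADS and EQ-5D-3L are not among the secondary outcomes in F1, so this point gives no ground for extending it to them.

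Cost: mostly wording, since no new instrument is needed. Women without a pre-delivery EPDS drop out of the adjusted analysis, so their number should be reported. Securing the baseline may also require a small change in when the survey is given. The adjusted logistic OR will have a slightly wider interval than the crude one.
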